The study has three aims (see Page 5) and involves a clustered randomized controlled trial (RCT) where K-5 elementary schools will be the unit of randomization. Aim 2 includes a clustered RCT conducted in YSD elementary schools to evaluate the effect of risk communication on COVID-19 testing uptake and school attendance. We will assess primary outcome (i.e., school attendance and COVID-19 testing uptake) on students; parent/guardian will provide informed consent through either an online, paper, or telephone process to enroll in the study. Following consent, parent/guardians of participants will receive instructions on study procedures and complete the enrollment questionnaire either via online through Project REDCap, on paper, or over the telephone with a study staff member. If the students attend a school that is randomized into the intervention group, they will receive the risk communication as three comic books and their parents will receive two videos at regular intervals throughout the study in English and Spanish. The risk communication will highlight benefits of and address barriers to preventative behaviors, SARS-CoV-2 testing, and COVID-19 vaccines. Participants in the comparison group will receive the risk communication comic books and videos at the end of the study as part of the delayed intervention. All participants will receive weekly brief reminders to complete an online Symptom/Exposure check-in in REDCap and encouraged to complete weekly testing at the YSD static testing site. Secondary outcome measures will be assessed for one index child in all families who have children enrolled in the study. Post

All students in the YSD have access to the District's COVID-19 static testing site. Screening and symptomatic testing will be available (but not mandated) to YSD students through the static site.

A partnership with the YSD will give permission to our team to access the school attendance data and SARS-CoV-2 test results on students enrolled in our research study. The agreement will also include access to de-identified SARS-CoV-2 test data from the static site. Access to student COVID-19 testing data will allow our team to examine the effect of risk communication on COVID-19 testing, primary outcomes (i.e., school attendance and COVID-19 testing participation), and secondary outcomes (i.e., physical activity, mental health, and COVID-19 vaccination) in this study.

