### Aim 2 Study Procedures:

Families will have three options to enroll children in the study: online through a website portal (Project REDCap), through a paper enrollment packet that will be distributed by our staff to students at school, or with assistance from study staff over the phone.

[figure not shown]
- Parents/guardians who choose to enroll children in the study online will provide informed consent by reading and e-signing consent and assent forms through a web-based REDCap portal, and then the participant's parent/legal guardian will complete a baseline enrollment questionnaire.
- The paper enrollment packet will include a flyer advertising the study, a guide for filling out the packets, consent and assent forms, and the enrollment questionnaire. Parents who prefer to enroll their child with the paper enrollment packets will fill out the enrollment packet and their child will return the completed packet to a secure lock box available at school. Study staff will pick up the consent enrollment packets from the lock box and enter the participant's information into REDCap. If there is information missing or issues with the paperwork, a staff member will call or email the parent of the participant to collect any missing information from their paper packet.
- Parents/guardians who choose to enroll with staff assistance over the phone will be verbally guided through the REDCap consent/assent forms and enrollment questionnaire.

Upon enrollment, randomization will occur per plan below:

**RCT Randomization Plan:** The randomization plan was developed by the study biostatistician. The schools will be matched in pairs with the primary match guided by the population of English Language Learners in the elementary schools and the secondary match on the size of the schools. The proportion of English Language Learners is highly correlated with low income and migrant status so will serve as a surrogate for all three characteristics. Size is moderately correlated to the proportion of English Language Learners. Once the study launches, each school within a pairing will be randomly assigned to either the Control or Intervention group.

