## 2. Study Schema and objectives

[figure not shown]
Purpose:	To determine the effectiveness of risk communication for parents and students on students' attendance to school, COVID-19 testing and vaccine uptake
Design:	A clustered randomized controlled trial of risk communication intervention
Central Hypotheses:	Our central hypotheses are that students and parents who view the risk communications will be more likely to have less school absence, increased covid-19 testing and vaccine uptake.
Primary Objectives:	

• To determine if implementing three COVID-19 education comic books for children and two COVID-19 education videos for parents will lower school absenteeism, increase COVID-19 testing, and vaccine uptake in children.

Secondary Objectives:	

• To determine if implementing three COVID-19 education comics books for children and two COVID-19 education videos for parents will increase physical activity, improve sleep, increase emotional regulation in children.

• To determine if implementing three COVID-19 education comics books for children and two COVID-19 education videos for parents will increase physical activity, improve sleep, decrease depression and anxiety in parents

Population:	Children ages 5-13 enrolled in kindergarten to 5 th grade in Yakima School District
Study Size:	14 schools randomized; 7 to intervention and 7 to comparison arms with 450 children in each arm; a total of 900 children from 14 schools.
Primary Outcome Measurements:	

A. Attendance captured through the school district

B. COVID-19 testing data available through the school district testing program and self-reported survey

C. COVID-19 vaccine data available through self-reported survey

Study Duration:	2 years including enrollment period, 2 months to deliver the intervention, 5 months for post 1 survey, 7 months weeks for post 2 survey.

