## 3. Study Design

ROSSEY study is a cluster randomized controlled trial to test COVID-19 risk communication intervention with 900 participants from 14 elementary schools in the Yakima School District during

the 2022-2023 school year. Schools are randomized 1:1 (matched by school size and English language learners) to either intervention or control group. Students and parents randomized to the intervention group receive the COVID-19 risk communication intervention. Students and parents randomized to the control group receive the same risk communication intervention at the end of the study as a delayed intervention.

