### Study Timeline

## 4. Sample size and power

**For month 5 outcome.** We will enroll 900 elementary school students from 14 schools in the Yakima School District during the 2022-2023 school year. The sample size of 7 schools per study arm and an average of 50 students per school will provide 90% power to detect a difference of at least 4 hours per week ( $SD=8.0$ ) of in-person school attendance between the intervention and control groups, while assuming intra-cluster correlation (ICC) of 0.05 and type I error rate of 0.05. The estimated sample size of 14 schools with 900 students provides 80% power to detect a difference of 20% or more in COVID-19 vaccination rates between the two study arms, assuming ICC of 0.05 and type I error rate of 0.05.

Minimum detectable difference in hours per week between intervention arms in proposed cluster RCT assuming enrollment of 15 students per classroom, 80% power and two-sided type I error rate of 0.05.					
		Two Arm			
	Number of clusters per arm	30		40	
	ICC	.01	.10	.01	.10
Standard Deviation	5.0	1.0	1.5	.87	1.3
	7.5	1.5	2.2	1.3	1.9

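### The detectable-difference table in SAP section 4 counts classrooms as randomised clusters, but the trial randomises 7 schools per arm

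*SAP*

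**What the plan says.** Both documents make the school the unit of allocation. The Protocol Summary states that "K-5 elementary schools will be the unit of randomization", and the randomisation plan under Aim 2 Study Procedures adds that "each school within a pairing will be randomly assigned to either the Control or Intervention group". SAP section 3 agrees: "Schools are randomized 1:1 (matched by school size and English language learners) to either intervention or control group". SAP section 2 gives the size: "14 schools randomized; 7 to intervention and 7 to comparison arms with 450 children in each arm".

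SAP section 4 then uses two different bases.

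- **The paragraph** counts schools: "The sample size of 7 schools per study arm and an average of 50 students per school will provide 90% power" for a difference of 4 hours per week with SD 8.0, "while assuming intra-cluster correlation (ICC) of 0.05 and type I error rate of 0.05". The same paragraph opens with "We will enroll 900 elementary school students from 14 schools in the Yakima School District".
- **The table** below it counts classrooms, "assuming enrollment of 15 students per classroom, 80% power and two-sided type I error rate of 0.05". It has 30 or 40 clusters per arm, ICC .01 or .10, and SD 5.0 or 7.5. The printed differences run from .87 to 2.2 hours per week. It does not say whether the ICC acts between classrooms or between schools.

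**The concern.** Classrooms in one school all receive the same allocation, so they are not independent randomised units. A table that treats them as such has two faults. It takes far more degrees of freedom than 14 schools provide, and it leaves out any correlation between pupils of different classrooms in the same school. Both make the detectable differences look smaller than they are.

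The table carries no label marking it as illustrative. It is headed as applying to the proposed cluster trial and stands in the sample size section. A reader would conclude that differences of about 1 to 2 hours per week can be detected with 80% power, and might judge a null or small result against those figures.

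**Working it through.** **Inputs.** From SAP section 4: 15 students per classroom, 30 or 40 clusters per arm, ICC .01 or .10, SD 5.0 or 7.5, 80% power, two-sided 0.05; and in the paragraph, 7 schools per arm, 50 per school, SD 8.0, ICC 0.05, 4 hours. From SAP section 2: 7 schools and 450 children per arm.

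**Formula.** For k clusters per arm of size m, SE = SD × √[2(1 + (m − 1)ICC)/(km)]. The detectable difference is the value that gives 80% power under the noncentral t with 2(k − 1) degrees of freedom. That is about 2.85 × SE on 58 df, 2.84 × SE on 78 df and 3.05 × SE on 12 df.

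**1. The table as printed.** Take m = 15 and k = 30 or 40, so df = 58 or 78. For SD 5, ICC .01, k = 30: SE = 5 × √(2 × 1.14/450) = 0.356, and the detectable difference is 1.014. The full set, in the order SD 5 ICC .01, SD 5 ICC .10, SD 7.5 ICC .01, SD 7.5 ICC .10:

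- 30 clusters: 1.014, 1.471, 1.521, 2.207 (printed 1.0, 1.5, 1.5, 2.2)
- 40 clusters: 0.874, 1.269, 1.311, 1.903 (printed .87, 1.3, 1.3, 1.9)

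All eight match after rounding. The arithmetic is right for randomised classrooms. Since 30 × 15 = 450 and 40 × 15 = 600, the 40-cluster columns also exceed the planned 450 per arm.

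**2. The paragraph as printed.** With k = 7, m = 50, SD 8, ICC 0.05: SE = 8 × √(2 × 3.45/350) = 1.123. Power for 4 hours on 12 df is 90.4%; a normal approximation gives 94.5%. The stated 90% is therefore what schools as clusters with 12 df give, and the same basis is applied to the table below.

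**3. The table on 7 schools per arm, 12 df, same number of children (N) per arm as each column.** The level of the ICC is not stated, so three readings are shown.

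- (a) ICC between schools: m = N/7, which is 64.3 or 85.7.
- (b) ICC between classrooms only, none between schools: SE = SD × √[2(1 + 14 ICC)/N].
- (c) The table's .10 within classroom with the paragraph's 0.05 within school: SE = SD × √[2(1 + 14 × 0.10 + (J − 1) × 15 × 0.05)/N], where J = N/105 classrooms per school. The .01 columns cannot be paired with 0.05 in this way, because under nested school and classroom effects classmates cannot correlate less than schoolmates.

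Too low = 1 − printed/recomputed.

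| Clusters | SD | ICC | Printed | (a) | too low | (b) | too low | (c) | too low |
|---|---|---|---|---|---|---|---|---|---|
| 30 | 5 | .01 | 1.0 | 1.300 | 23.1% | 1.086 | 8.0% | – | – |
| 30 | 5 | .10 | 1.5 | 2.755 | 45.5% | 1.576 | 4.8% | 2.244 | 33.2% |
| 30 | 7.5 | .01 | 1.5 | 1.950 | 23.1% | 1.630 | 8.0% | – | – |
| 30 | 7.5 | .10 | 2.2 | 4.132 | 46.8% | 2.365 | 7.0% | 3.366 | 34.6% |
| 40 | 5 | .01 | .87 | 1.198 | 27.4% | 0.941 | 7.5% | – | – |
| 40 | 5 | .10 | 1.3 | 2.712 | 52.1% | 1.365 | 4.8% | 2.147 | 39.4% |
| 40 | 7.5 | .01 | 1.3 | 1.797 | 27.6% | 1.411 | 7.9% | – | – |
| 40 | 7.5 | .10 | 1.9 | 4.068 | 53.3% | 2.048 | 7.2% | 3.220 | 41.0% |

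Against the planned 450 per arm, the 40-cluster values under (a) are 33–54% too low.

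**4. Power at the printed differences, 450 per arm, 12 df.**

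| Reading | 30-cluster cells | 40-cluster cells |
|---|---|---|
| (a) | 58, 33, 58, 32% | 47, 26, 47, 25% |
| (b) | 73, 76, 73, 74% | 61, 64, 61, 62% |
| (c), ICC .10 only | 47, 45% | 37, 35% |

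Simulation of 40,000 trials per case, with 30 classrooms spread over 7 schools per arm, agrees: 58% and 33% under (a), 73% under (b), 47% and 45% under (c).

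**5. Students per school.** 14 × 50 = 700, whereas 900/14 = 64.3. At 64.3 per school the power for 4 hours is 92.1% instead of 90.4%, so this slip is conservative.

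**The case against.** The strongest point is that nothing rests on the table. The sample size comes from the paragraph, the Protocol's Sample Size section likewise relies only on 4 hours, and every cell is correct for the classroom design in the caption. This is a mismatch between table and design, not a slip of calculation. That stands, and it is why the point is minor.

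The size is also open to argument.

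- **Level of the ICC.** The caption's only unit is the classroom, so reading (b) is the natural one, and (a) is an upper case in which classmates resemble each other no more than schoolmates do. That is fair. But (b) needs zero correlation between schools, which conflicts with the 0.05 that the same section assumes for 7 schools per arm and with the school random effect in the SAP's primary model (section 12.c.ii).
- **Reference distribution.** The SAP names no degrees-of-freedom method. With a normal approximation, (b) gives 0.997, 1.447, 1.496, 2.170 and 0.864, 1.253, 1.295, 1.879, all at or below print, so the 5–8% disappears. Under (a) the same approximation still leaves 16–42% and 21–49%. The SAP's own 90% figure reproduces on 12 df, so 12 df is the better basis, but the conclusion must be read with that condition.
- **Sample size in the power figures.** The 40-cluster power figures above combine two effects, the unit of randomisation and the loss of 150 children per arm. At 600 per arm they are 73–76% under (b) and 53, 27, 53, 26% under (a).
- **Rounding.** The 5–8% spread partly reflects rounded cells; on unrounded values it is about 7% throughout.
- **Matching.** Any gain in precision from pairing schools is not modelled. A paired test on 6 df without such a gain would widen the ranges under (a) to 30–52% and 34–58%. The net effect is unknown.

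**Conclusion.** The concern holds. The table claims 80% power for a design in which classrooms are randomised, and the trial does not have that design. At equal numbers of children the printed differences are 5–8% too low if all correlation lies between classrooms, and 23–47% (30 clusters) or 27–53% (40 clusters) too low if the table's ICCs lie between schools. Combining the table's .10 with the paragraph's 0.05 gives 33–35% and 39–41%.

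With the planned 450 per arm and a t test on 12 df, none of the three readings reaches 80% power at the printed values. Power is 61–76% in the mildest reading and 25–58% with between-school ICCs. These figures assume an unpaired comparison, equal school sizes and no gain from matching.

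The 90% power statement for 4 hours is sound. This is a correction of stated figures that should be made; it does not challenge the sample size.

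**What to change.** Delete the table, or replace it with one for 7 schools per arm at about 64 students per school, stating that the ICC is between schools and that 12 df are used. For the paragraph's SD of 8 the detectable differences at 80% power are 2.1, 3.3 and 4.4 hours per week at school ICC 0.01, 0.05 and 0.10.

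Reconcile the 50 students per school with the stated 900, which is 64.3 per school. Keep the 90% power statement for 4 hours.

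The cost is one table and one phrase in SAP section 4. The stated detectable differences become less favourable. No extra enrolment is needed, and the design and analysis stay as they are.

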## 5. Population and Data Source

Participants enrolled in the ROSSEY Study: 900 children and parents from the Yakima School District. Any randomized participants subsequently found to be ineligible will be removed. The data sources for the primary analyses are the attendance records and positive COVID testing results received from the school administration and the survey data as entered in REDCap. COVID Vaccination status data is obtained through the parent and child surveys that are completed in REDCap.

## 6. Presentation of comparative analyses

For each of the continuous outcomes (including the primary outcome), the mean and standard deviation for each allocated group will be presented, together with the mean between-group difference, 95% confidence interval for the difference and p value. For binary outcomes, the percentage and frequency of children in the outcome category of interest (e.g. percentage vaccinated) will be presented for each allocated group, along with the odds ratio for the intervention effect, 95% confidence interval for the odds ratio and p value.

## 7. Outcome Definitions

### a. Primary Outcomes

The three co-primary outcomes for the trial are school absenteeism, COVID-19 testing, and COVID-19 vaccine uptake. Absenteeism are the student's school attendance data for 2022-2023 school year, COVID-19 data are captured through school testing and self-reported survey, and COVID-19 vaccine uptake data are captured through self-reported survey. All children and parent data after randomization will be included in the intention to treat analysis.

**Absenteeism:** total number of school days missed by each individual student participant, both for the entire school year and month-by-month, as captured and shared with us by school district administrative data systems. Absenteeism will also be measured by school days missed and will be a count variable.

**COVID-19 testing:** Health reports from the school are provided for the 2021-2022 and 2022-2023 school year that list positive covid test results of study participants with the date of testing and the school of attendance. Positive COVID test results will be a binary yes/no variable.

**COVID-19 vaccine uptake:** Parents are asked at enrollment to report their vaccination status and their child's vaccination status. At post survey 1 and post survey 2 the parent is asked to report if they or their child have received any COVID-19 vaccine or booster since enrollment. Vaccination status will be a binary yes/no variable.

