The primary outcomes will be assessed on children and will include school absenteeism and participation in the SARS-CoV-2 testing (data obtained through administrative records). The secondary outcomes will capture physical activity, stress, depressive symptoms and COVID-19 vaccination among both enrolled children (by parent report) and parents or legal guardians of enrolled children. The goal is to conduct secondary outcome assessment surveys with 900 parents: 450 parents of children in the control group and 450 parents of children in the intervention group. The secondary outcome surveys will be completed for one index child per family, if more than one child in a household is enrolled in the study. The index child will be the child with the most recent birthday from time of household enrollment into the study. Parents will be asked to complete surveys about their own and their child's perceived stress, sleep disturbance, and emotional regulation. Parents will be invited to complete secondary outcome survey assessments at the time of enrollment, halfway through the study, and at the end of the study.

**Figure 1.** Timetable of overall study procedures

	Enrollment	Weekly	Study Post Survey 1 & Post Survey 2	Once a month after enrollment closed	Final Aim 2 data collection
Electronic, Phone or Paper Consent/Accent	X				
Electronic, Phone or Paper Enrollment Questionnaire	X				
Weekly Check-In Survey		X			
Update survey collecting changes in COVID-19 vaccination status and mitigation behaviors such as masking			X		X
Secondary outcomes (physical activity, perceived stress, COVID-related stress, and depressive symptomatology for parents	X		X		X
Intervention Group: Risk communication comic books/videos (n=3)				X	

distributed to children at school and parent videos (n=2) distributed by link in email					
Control Group: receives risk communication at the end of the school year (delayed intervention)					X

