**After enrollment is complete, parents/guardians of study participants will take part in the following study procedures:**

**Figure 2. Outline of Study Procedures**

**Weekly Check-in Survey:** Parents of enrolled students will be asked to complete an online weekly 5-minute survey throughout the duration of the study that asks if their child is experiencing symptoms consistent with COVID-19 and has sought health care, if they have been absent from school in the past week, or if they have been exposed to someone with suspected COVID-19. Parents will also be asked if their child has been tested for SARS-CoV-2 at the Yakima School district static test site.

**Secondary Outcome Assessments:** Participants will be asked to participate in secondary outcome assessment surveys for the index child in each family collected either online, on paper, or by phone, based on their preferences. The index child will be selected based on the child with the most recent birthday from the time of enrollment if there is more than one child enrolled in a family. The goal is to conduct 900 secondary outcome assessments: 450 parents of children in the intervention group and 450 parents of children in the control group. Study surveys are available in both English and Spanish, as chosen by the participating parent or guardian.

Parents will be asked to complete surveys on topics such as their own and their child's perceived stress, sleep disturbance, physical activity, and emotional regulation (including both depressive and anxiety symptoms). Secondary outcome survey assessments will be offered to participants to be completed at the time of enrollment, halfway through the study (month 4), and at the end of the study (month 6). In order to better understand potential moderators and mediators of intervention effects, these surveys will also assess health literacy (at enrollment only), positive and negative outcomes expectations around testing and vaccines, and self-efficacy around testing, mask use, discussing COVID-19 with a healthcare provider and risk communication/information relevancy.

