#### i. Descriptive Analyses:

Positive COVID test results from the school district testing program will be summarized by counts by randomization group. Vaccine status and covid testing results will be summarized by counts and percentages by randomization group. Continuous variables by mean, standard

deviation(SD) and median (IQR) by randomization group. Secondary outcomes will be summarized and compared using Chi-squared tests

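### The SAP names two data sources for the testing co-primary, defines it from one, and gives no rule for combining them or for coding a child without survey data

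*SAP*

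**What the plan says.** The protocol (III. Study Design, Aim 2) lists as a primary outcome "participation in the SARS-CoV-2 testing (data obtained through administrative records". Its Weekly Check-in Survey (V. Study Procedures, Aim 2) also covers testing: "Parents will also be asked if their child has been tested for SARS-CoV-2 at the Yakima School district static test site". The protocol does not name that item as the source of the primary outcome.

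The SAP is not consistent with this or with itself:

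- Section 2, Primary Outcome Measurements: "COVID-19 testing data available through the school district testing program and self-reported survey".
- Section 7.a, opening paragraph: "COVID-19 data are captured through school testing and self-reported survey".
- Section 7.a, detailed definition: "Health reports from the school are provided for the 2021-2022 and 2022-2023 school year that list positive covid test results of study participants", then "Positive COVID test results will be a binary yes/no variable". The survey is not mentioned here.
- Section 5, sources for the primary analyses taken together: "positive COVID testing results received from the school administration and the survey data as entered in REDCap".
- Section 12.c.i: "Positive COVID test results from the school district testing program will be summarized by counts by randomization group". A separate sentence then covers COVID testing results, by counts and percentages.
- Section 12.c.ii: positive results go into a mixed logistic model with school random effects.

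On missing data, Section 12.c marks missing responses as loss to follow-up when a post survey closes. Section 11 plans multiple imputation as a sensitivity analysis and otherwise promises unspecified suitable methods. Nowhere is there a rule for combining the two testing sources, or for a child whose parent gave no survey data.

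**The concern.** District records do not depend on whether a parent answers study surveys. Survey reports do. If both feed one binary variable, a child whose parent keeps responding has two routes to a "yes", and a child whose parent stops has one. The co-primary then partly measures survey participation.

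This matters for the arm comparison only if response differs by arm. That is plausible but not shown. During follow-up only the intervention arm receives comic books and video links from the study; the comparison arm receives them at the end.

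The ambiguity is compounded by what a "yes" means. The protocol outcome is participation in testing, and SAP 2 hypothesises more testing. SAP 7.a defines a positive result, and SAP 12.c.ii hypothesises lower infection rates. A spurious excess of "yes" in one arm would count for the intervention under one reading and against it under the other.

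**Working it through.** **Plan figures.** The documents give no event rate, survey-only share, response rate or power for the testing co-primary, so there is no figure to reproduce for this outcome. The nearest is the attendance power in SAP 4 (7 schools per arm, 50 students per school, difference 4, SD 8.0, ICC 0.05). Design effect 1 + 49 × 0.05 = 3.45; effective n per arm 350 / 3.45 = 101.4; a noncentral t with 12 df gives 90.4%, matching the stated 90%. Only its ICC is used below.

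**Assumptions, for illustration.** No true effect. District-recorded share a = 5%. Share that only a survey would find, b = 10% or 5%. Response r is unrelated to testing and is 70% vs 60%, or 80% vs 60%, intervention vs comparison.

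**Coding A: "yes" if either source says so, non-response counted as "no".** P(yes) = a + b·r.

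- b = 10%, 70 vs 60: 0.05 + 0.10 × 0.7 = 0.120 vs 0.110; OR = (0.120/0.880)/(0.110/0.890) = 1.10.
- b = 10%, 80 vs 60: 0.130 vs 0.110; OR 1.21.
- b = 5%, 70 vs 60: 0.085 vs 0.080; OR 1.07.
- b = 5%, 80 vs 60: 0.090 vs 0.080; OR 1.14.

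**Coding B: as A, but a non-responder not on the district list is missing.** The number of "yes" is unchanged; the denominator is r + (1 − r)·a, which is 0.715, 0.620 and 0.810 for r = 0.7, 0.6 and 0.8.

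- b = 10%, 70 vs 60: 0.120/0.715 vs 0.110/0.620; OR = (0.120/0.595)/(0.110/0.510) = 0.94.
- b = 10%, 80 vs 60: (0.130/0.680)/(0.110/0.510) = 0.89.
- b = 5%, 70 vs 60: (0.085/0.630)/(0.080/0.540) = 0.91.
- b = 5%, 80 vs 60: (0.090/0.720)/(0.080/0.540) = 0.84.

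The same data give a false increase under A and a false decrease under B.

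**Coding C: every non-responder missing, even if on the district list.** P(yes) = (a + b)·r / r = a + b in both arms, so OR = 1. This relies on response being unrelated to testing, and it discards known district results.

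**District records only.** P(yes) = a in both arms whatever r is; OR = 1.

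**Equal response.** The arms are identical under every coding; OR = 1.

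**Wider range for coding A.** Write the observed rate as p(1 − s·d), with p the true rate, s the share of "yes" found only by survey, and d the drop-out. For p from 0.2 to 0.6 and s from 0.25 to 0.75, drop-out of 20% vs 10% gives false ORs of 1.03 to 1.20, and 30% vs 10% gives 1.07 to 1.44. The upper end is 0.6(1 − 0.75 × 0.1) = 0.555 vs 0.6(1 − 0.75 × 0.3) = 0.465.

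**Benchmark.** With 450 per arm in 7 schools (64.3 per school) and ICC 0.05 borrowed from SAP 4, the design effect is 1 + 63.3 × 0.05 = 4.16 and effective n is 450 / 4.16 = 108. At a rate of 12%, the SE of the difference is √(2 × 0.12 × 0.88 / 108) = 4.4 points. The four coding A differences are 0.5 to 2.0 points, so the largest is under half an SE.

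**The case against.** The strongest reply is that the operative definition in SAP 7.a uses school reports only, and that the model and the first descriptive sentence refer to positive results. On that reading survey drop-out cannot touch the outcome. This is a fair reading, but SAP 2 and the opening of 7.a contradict it, and an analyst cannot tell which governs. SAP 5 does not settle it: its survey data may refer to vaccination alone, which the next sentence takes up.

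A reader might go further and infer that a child whose parent stops answering is recorded as "no", so that imputation never sees a missing value. The documents do not support this as a statement of the plan. No merge rule is written, SAP 12.c marks post-survey non-response as loss to follow-up, and SAP 11 plans imputation as a sensitivity analysis. Absence from a positives-only list does read as "no", but for responders and non-responders alike; it links to survey response only if a second source can overturn it. Equally, SAP 12.c does not close the gap. It concerns the post surveys, whereas the only testing question described is in the weekly check-in.

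Other points stand and limit the size. The check-in asks about the same district site that mainly supplies the records, so the true survey-only share may be well below the 5% to 10% assumed. Reminders go to all participants, the $5 and $50 gift cards are described without distinction by arm, and home visits pursue follow-up survey non-responders still in the district. Differential response is therefore a possibility, not a finding.

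**Conclusion.** The point holds as a conflict over the data source of a co-primary outcome, with no combination rule and no coding rule for absent survey data. It does not hold as a demonstrated bias. If the sources are merged and response differs by arm, a false arm difference can follow: OR about 1.07 to 1.21 with non-response coded "no", or about 0.84 to 0.94 with unlisted non-responders coded missing. These figures rest entirely on the assumed shares and response rates, and would shrink with a smaller survey-only share. In the 5% and 10% examples the false difference under "no" coding is small against sampling error. The reason to act is that the rule left open can decide even the direction of the artefact, and a district-only definition removes the dependence. Confidence is moderate.

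**What to change.** In SAP 2, 5 and 7.a:

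1. Define the testing co-primary from district records only, for the time the child is enrolled in the Yakima School District, in line with the protocol's Aim 2 text.
2. State whether the variable is participation in testing (protocol, Aim 2) or a positive result (SAP 7.a and 12.c.ii), and align the hypothesis and model. Reports listing only positives cannot measure participation. If that is the outcome, use the test information on enrolled children covered by the data agreement (protocol IX), and confirm that the district will supply tests taken and not just positives.
3. Move self-reported tests to a supportive analysis among completed weekly check-ins, with the number completed as the denominator, and report check-in completion by arm.

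The source change is SAP wording only; choosing participation also requires confirming the data supply. Tests known only from parents would no longer count in the co-primary, so its event rate may be slightly lower. The loss should be small, because the check-in item asks about the same testing site.
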